5.4 Patient Demographics and Frequency of Adverse Drug Reactions / Infections by Treatment

5.4.1 Patients demographics and Frequency of Adverse Drug Reactions / Infections by Treatment

(1) Patients to be tabulated and analyzed

Safety Analysis Set

(2) Details of tabulation and analysis

Each parameter will be categorized by the categories described below to tabulate the percent of patients with adverse drug reactions, etc.

The Fischer exact test will be used for parameters without rank data. The Mann-Whitney U test will be used for parameters with rank data. (The tests will be used for parameters with asterisk [*].)

Total and mild type 2 diabetes mellitus patients will be tabulated.

Parameter	Category
Sex*	Male, Female
Age*	< 65 years, ≥65 years
	< 75 years, ≥75 years
Severity of renal impairment*	Normal + Mild, Moderate + Severe
Concurrent liver disorder*	No, Yes
Concurrent renal disorder*	No, Yes
Concurrent heart disease*	No, Yes

Parameter	Category
Details of concurrent heart disease (overlapped)	Cardiac failure, myocardial infarction, or angina pectoris
Concurrent cardiac failure*	No, Yes
Severity classification of cardiac failure (NYHA classification)*	Classes NYHA I, NYHA II, NYHA III, and NYHA IV
Concurrent stroke-related disease*	No, Yes
Mean daily dose of Nesina	> 25 mg, 25 to >12.5 mg, 12.5 to > 6.25 mg, or ≤6.25 mg
Administration of concomitant medication (diabetic drug)	No, Yes
Concomitant medications (diabetic drugs) (overlapped)	α-glucosidase inhibitors, thiazolidines, sulfonylureas, biguanides, rapid-acting insulin secretagogues, or insulin preparations
Administration of concomitant medication (protease drug)*	No, Yes
Administration of concomitant medication (combined with renal excretory drug)*	No, Yes

(3) Number of tables and figures

Table 5.4.1-1

5.5 Occurrence of Adverse Drug Reactions / Infections by Age

(1) Patients to be tabulated and analyzed

Safety Analysis Set

(2) Details of tabulation and analysis

Age will be classified into < 65 years, ≥65 years and < 75 years, and ≥75 years for tabulation of type of adverse drug reactions, etc.

The method for tabulation of adverse drug reactions, etc. is same as that described in Section 5.1.

Total and mild type 2 diabetes mellitus patients will be tabulated.

(3) Number of tables and figures

Tables 5.5-1 to 5.5-2

5.6 Occurrence of Adverse Drug Reactions / Infections by Sex

(1) Patients to be tabulated and analyzed

Safety Analysis Set

(2) Details of tabulation and analysis

Sex will be classified into male or female for tabulation of type of adverse drug reactions, etc.

The method for tabulation of adverse drug reactions, etc. is same as that described in Section 5.1.

Total and mild type 2 diabetes mellitus patients will be tabulated.

(3) Number of tables and figures

Table 5.6-1

5.7 Occurrence of Adverse Drug Reactions / Infections by Liver Disorder

(1) Patients to be tabulated and analyzed

Safety Analysis Set

(2) Details of tabulation and analysis

Concurrent liver disorder will be classified into yes or no for tabulation of type of adverse drug reactions, etc.

The method for tabulation of adverse drug reactions, etc. is same as that described in Section 5.1.

Total and mild type 2 diabetes mellitus patients will be tabulated.

(3) Number of tables and figures

Table 5.7-1

5.8 Occurrence of Adverse Drug Reactions / Infections by Presence of Concurrent Renal Disorder

(1) Patients to be tabulated and analyzed

Safety Analysis Set

(2) Details of tabulation and analysis

Concurrent renal disorder will be classified into yes or no for tabulation of type of adverse

drug reactions, etc.

The method for tabulation of adverse drug reactions, etc. is same as that described in Section 5.1.

Total and mild type 2 diabetes mellitus patients will be tabulated.

(3) Number of tables and figures

Table 5.8-1

5.9 Occurrence of Adverse Drug Reactions / Infections by Severity of Renal Impairment

(1) Patients to be tabulated and analyzed

Safety Analysis Set

(2) Details of tabulation and analysis

Severity of renal impairment will be classified into normal + mild or moderate + severe for tabulation of type of adverse drug reactions, etc.

The method for tabulation of adverse drug reactions, etc. is same as that described in Section 5.1.

Total and mild type 2 diabetes mellitus patients will be tabulated.

(3) Number of tables and figures

Table 5.9-1

5.10 Occurrence of Adverse Drug Reactions / Infections by Presence of Concurrent Heart Disease

(1) Patients to be tabulated and analyzed

Safety Analysis Set

(2) Details of tabulation and analysis

Concurrent heart disease will be classified into yes or no for tabulation of type of adverse drug reactions, etc.

The method for tabulation of adverse drug reactions, etc. is same as that described in Section 5.1.

Total and mild type 2 diabetes mellitus patients will be tabulated.

(3) Number of tables and figures

Table 5.10-1

5.11 Occurrence of Adverse Drug Reactions / Infections by Presence of Concurrent Heart Failure

(1) Patients to be tabulated and analyzed

Safety Analysis Set

(2) Details of tabulation and analysis

Concurrent heart failure will be classified into yes or no for tabulation of type of adverse drug reactions, etc.

The method for tabulation of adverse drug reactions, etc. is same as that described in Section

5.1.

Total and mild type 2 diabetes mellitus patients will be tabulated.

(3) Number of tables and figures

Table 5.11-1

5.12 Occurrence of Adverse Drug Reactions / Infections by Severity of Heart Failure

(1) Patients to be tabulated and analyzed

Safety Analysis Set

(2) Details of tabulation and analysis

Severity of heart failure will be classified into Class NYHA I, NYHA II, NYHA III, or NYHA IV for tabulation of type of adverse drug reactions, etc.

The method for tabulation of adverse drug reactions, etc. is same as that described in Section 5.1.

Total and mild type 2 diabetes mellitus patients will be tabulated.

(3) Number of tables and figures

Table 5.12-1

5.13 Occurrence of Adverse Drug Reactions / Infections by Presence of Concurrent Stroke-related Disease

(1) Patients to be tabulated and analyzed

Safety Analysis Set

(2) Details of tabulation and analysis

Concurrent stroke-related disease will be classified into yes or no for tabulation of type of adverse drug reactions, etc.

The method for tabulation of adverse drug reactions, etc. is same as that described in Section 5.1.

Total and mild type 2 diabetes mellitus patients will be tabulated.

(3) Number of tables and figures

Table 5.13-1

5.14 Occurrence of Adverse Drug Reactions / Infections by Mean Daily Dose of Nesina

(1) Patients to be tabulated and analyzed

Safety Analysis Set

(2) Details of tabulation and analysis

The mean daily dose of Nesina will be classified into > 25 mg, 25 to > 12.5 mg, 12.5 to > 6.25 mg, or ≤6.25 mg for tabulation of type of adverse drug reactions, etc.

The method for tabulation of adverse drug reactions, etc. is same as that described in Section

5.1.

Total and mild type 2 diabetes mellitus patients will be tabulated.

(3) Number of tables and figures

Table 5.14-1

5.15 Occurrence of Adverse Drug Reactions / Infections by Mean Daily Dose of Nesina in Patients with Special Demographics (Patients with Moderate or Higher Renal Impairment)

(1) Patients to be tabulated and analyzed

Patients with moderate or higher renal impairment in the Safety Analysis Set

(2) Details of tabulation and analysis

The mean daily dose of Nesina will be classified into > 25 mg, 25 to > 12.5 mg, 12.5 to > 6.25 mg, or ≤6.25 mg for tabulation of type of adverse drug reactions, etc.

The method for tabulation of adverse drug reactions, etc. is same as that described in Section 5.1.

Total and mild type 2 diabetes mellitus patients will be tabulated.

(3) Number of tables and figures

Table 5.15-1

5.16 Occurrence of Adverse Drug Reactions / Infections by Administration of Concomitant Medication (Diabetic Drug)

(1) Patients to be tabulated and analyzed

Safety Analysis Set

(2) Details of tabulation and analysis

Administration of concomitant medication (diabetic drug) will be classified into yes or no for tabulation of type of adverse drug reactions, etc.

The method for tabulation of adverse drug reactions, etc. is same as that described in Section 5.1.

Total and mild type 2 diabetes mellitus patients will be tabulated.

(3) Number of tables and figures

Table 5.16-1

5.17 Occurrence of Adverse Drug Reactions / Infections by Concomitant Medication (Diabetic Drug)

(1) Patients to be tabulated and analyzed

Safety Analysis Set

(2) Details of tabulation and analysis

Concomitant medications (diabetic drugs) will be classified into the following drugs: α -glucosidase inhibitors, thiazolidines, sulfonylureas, biguanides, rapid-acting insulin

secretagogues, or insulin preparations, for tabulation of type of adverse drug reactions, etc.

The method for tabulation of adverse drug reactions, etc. is same as that described in Section 5.1.

Total and mild type 2 diabetes mellitus patients will be tabulated.

(3) Number of tables and figures

Table 5.17-1

5.18 Occurrence of Adverse Drug Reactions / Infections by Presence of Concomitant Protease Inhibitors

(1) Patients to be tabulated and analyzed

Safety Analysis Set

(2) Details of tabulation and analysis

Concomitant protease inhibitor will be classified into yes or no for tabulation of type of adverse drug reactions, etc.

The method for tabulation of adverse drug reactions, etc. is same as that described in Section 5.1.

Total and mild type 2 diabetes mellitus patients will be tabulated.

(3) Number of tables and figures

Table 5.18-1

5.19 Occurrence of Adverse Drug Reactions / Infections by Presence of Concomitant Renal Excretory Drug

(1) Patients to be tabulated and analyzed

Safety Analysis Set

(2) Details of tabulation and analysis

Concomitant renal excretory drug be classified into yes or no for tabulation of type of adverse drug reactions, etc.

The method for tabulation of adverse drug reactions, etc. is same as that described in Section 5.1.

Total and mild type 2 diabetes mellitus patients will be tabulated.

(3) Number of tables and figures

Table 5.19-1

5.20 Change in Laboratory/Measured Data

5.20.1 Vital Signs

(1) Patients to be tabulated and analyzed

Safety Analysis Set

(2) Details of tabulation and analysis

For blood pressure (systolic/diastolic) and weight, summary statistics will be calculated at each testing time point (start of Nesina treatment, 3 months, 6 months, 12 months, 18 months, 24 months, 30 months, and 36 months after Nesina treatment and last evaluation). For changes from the start of Nesina treatment, summary statistics and the mean 95% confidence intervals will be calculated.

Measured values (mean and standard deviation) of blood pressure (systolic/diastolic) and weight will be plotted. For the changes, the mean changes will be created using a bar graph.

Total and mild type 2 diabetes mellitus patients will be tabulated.

(3) Number of tables and figures

Table 5.20.1-1 and Figures 5.20.1-1 to 5.20.1-6

5.20.2 Laboratory Values

(1) Patients to be tabulated and analyzed

Safety Analysis Set

(2) Details of tabulation and analysis

For laboratory values of fasting triglyceride, total cholesterol, HDL-cholesterol, LDL-cholesterol, and non-HDL cholesterol, summary statistics will be calculated at each testing time point (start of Nesina treatment, 3 months, 6 months, 12 months, 18 months, 24 months, 30 months, and 36 months after Nesina treatment and last evaluation). For changes from the start of Nesina treatment, summary statistics and the mean 95% confidence intervals will be calculated.

The individual laboratory values described above (mean and standard deviation) will be plotted. For the changes, the mean changes will be created using a bar graph.

Total and mild type 2 diabetes mellitus patients will be tabulated.

(3) Number of tables and figures

Table 5.20.2-1 and Figures 5.20.2-1 to 5.20.2-10

6.0 Efficacy Tabulation and Analysis

6.1 Changes in HbA1c

(1) Patients to be tabulated and analyzed

Efficacy Analysis Set

(2) Details of tabulation and analysis

For HbA1c (NGSP values), summary statistics will be calculated at each testing time point (start of Nesina treatment, 3 months, 6 months, 12 months, 18 months, 24 months, 30 months, and 36 months after Nesina treatment and last evaluation). For changes, summary statistics and the mean 95% confidence intervals will be calculated and the paired t-test will be performed.

Measured values of HbA1c (NGSP values) will be plotted and for the changes a bar graph will be created excluding the unknown category at each testing time point (start of Nesina treatment, 3 months, 6 months, 12 months, 18 months, 24 months, 30 months, and 36 months after Nesina treatment and last evaluation).

(3) Number of tables and figures

Table 6.1-1 and Figure 6.1-1

6.2 Glycemic control achievement rate (HbA1c)

(1) Patients to be tabulated and analyzed

Efficacy Analysis Set

(2) Details of tabulation and analysis

The Glycemic control achievement rate for HbA1c (NGSP value) will be tabulated ($< 7.0\%$, $\geq 7.0\%$ / $< 6.0\%$, $\geq 6.0\%$) and a bar graph will be created ($< 7.0\%$, $\geq 7.0\%$ / $< 6.0\%$, $\geq 6.0\%$) at each testing time point (start of Nesina treatment, 3 months, 6 months, 12 months, 18 months, 24 months, 30 months, and 36 months after Nesina treatment and last evaluation) (the unknown category will be excluded for the bar graph).

(3) Number of tables and figures

Table 6.2-1 and Figure 6.2-1

6.3 Changes in Fasting blood glucose level and Fasting insulin level

(1) Patients to be tabulated and analyzed

Efficacy Analysis Set

(2) Details of tabulation and analysis

For fasting blood glucose level and fasting insulin level, summary statistics will be calculated at each testing time point (start of Nesina treatment, 3 months, 6 months, 12 months, 18 months, 24 months, 30 months, and 36 months after Nesina treatment and last evaluation). For changes, summary statistics and the mean 95% confidence intervals will be calculated and the paired t-test will be performed.

Measured values of fasting blood glucose level and fasting insulin level will be plotted and for the changes a bar graph will be created excluding the unknown category at each testing time point (start of Nesina treatment, 3 months, 6 months, 12 months, 18 months, 24 months, 30 months, and 36 months after Nesina treatment and last evaluation).

(3) Number of tables and figures

Tables 6.3-1 and 6.3-2 and Figures 6.3-1 and 6.3-2

6.4 Changes in HbA1c, etc. by Factor Probably Affecting Efficacy

(1) Patients to be tabulated and analyzed

Efficacy Analysis Set

(2) Details of tabulation and analysis

For changes in HbA1c (NGSP values), summary statistics and the mean 95% confidence intervals will be calculated and the paired t-test will be performed at each testing time point (start of Nesina treatment, 3 months, 6 months, 12 months, 24 months, and 36 months after Nesina treatment and last evaluation).

The Glycemic control achievement rate for HbA1c ($< 7.0\%$, $\geq 7.0\%$ / $< 6.0\%$, $\geq 6.0\%$) at each testing time point (start of Nesina treatment, 3 months, 6 months, 12 months, 24 months, and 36 months after Nesina treatment and last evaluation) will be tabulated at the following parameters:

i Sex (Male, Female)

ii Age (< 65 years, ≥ 65 years)

iii Age (< 75 years, ≥ 75 years)

iv Concurrent renal disorder (No, Yes)

v HbA1c (NGSP value) at the start of Nesina treatment ($< 6.0\%$, 6.0% to $< 7.0\%$, 7.0% to $< 8.0\%$, $\geq 8.0\%$)

vi Mean daily dose of Nesina (> 25 mg, 25 to > 12.5 mg, 12.5 to > 6.25 mg, or 6.25 mg)

vii Concomitant diabetic drugs (α -glucosidase inhibitors, thiazolidines, sulfonylureas, biguanides, rapid-acting insulin secretagogues, or insulin preparations)

(3) Number of tables and figures

Tables 6.4-1 to 6.4-14

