## 9.3 Survey sheet: details of treatment

### 1) Matters to be surveyed

Details of Nesina treatment (daily dose and administration period), status of end of Nesina treatment, reason for Nesina discontinuation (if applicable), details of other diabetic drug treatment\* (drug name, daily dose, route of administration, and administration period), and status of concomitant medications (other than diabetic drugs) (drug name, route of administration, administration period, and objectives of administration)

\* Diabetic drugs which are discontinued within 3 months prior to Nesina treatment are included.

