### 2) Survey period

Period from the start of Nesina treatment to 36 months after treatment (or treatment discontinuation)

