Patients with concurrent allergic dermatitis	Patients with concurrent disease of the PT Code 10012434 (dermatitis allergic).
Patients with concurrent malignant tumor	Patients with concurrent disease of the SOC Code 10029104 (neoplasms benign, malignant and unspecified (incl cysts and polyps)).
Patients with concurrent malignant tumor (narrow sense)	Patients with concurrent disease of the SMQ Code 20000194 (malignant tumour (SMQ) narrow).
Patients with other concurrent disease	Patients with concurrent disease other than the above (diabetic complication, hypertension, dyslipidaemia, hyperuricaemia, liver disease, renal disease, heart disease, stroke-related disease, allergic disease, malignant tumor, or malignant tumor (narrow sense)).
Severity of renal impairment	Severity of renal impairment in the patient demographic section

Term	Definition
Age	If the start month and date of Nesina treatment is earlier than the birth month and date, calculate using the following formula: Start year of Nesina treatment – birth year – 1. If the birth month and date is earlier than or equal to the start month and date of Nesina treatment, calculate using the following formula: Start year of Nesina treatment – birth year. For unknown birth date, the birth date will be calculated as the 1st day of the birth month.
BMI	Calculate using the following formula: Weight (kg) / (0.0001 × Height (cm) × Height (cm)). Indicate to one decimal place rounded from two decimals.
Disease duration of type 2 diabetes mellitus (year)	Calculate using the following formula: (start date of Nesina treatment – diagnosis period of type 2 diabetes mellitus + 1) / 365.25. For unknown diagnosis month, calculate as January. Indicate to one decimal place rounded from two decimals.
Prior medication	Medications that patients were taking within 3 months before initiation of Nesina therapy.
Concomitant medication	Medications that patients were taking after the start date of Nesina treatment.
Start date of other diabetic drug and concomitant medication (other than diabetic drug)	Calculate as the start date of survey sheet (electronic).
End date of other diabetic drug and concomitant medication (other than diabetic drug)	Calculate as the end date of survey sheet (electronic).
Diabetic drugs	Drugs of the National Health Insurance (NHI) Drug List Code starting with 3969, 3961, 3962, 2492, 2499410, 2499411, 2499415, or 2499416.

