4.0 Details of Treatment

(1) Patients to be tabulated and analyzed

Safety Analysis Set

(2) Details of tabulation and analysis

Each parameter will be classified by the categories described below to tabulate the number of patients and frequency.

Total and mild type 2 diabetes mellitus patients will be tabulated.

Parameter	Category
Initial dose of Nesina	25 mg, 12.5 mg, 6.25 mg, or other
Mean daily dose of Nesina	> 25 mg, 25 to >12.5 mg, 12.5 to > 6.25 mg, or ≤6.25 mg
Nesina treatment period	Summary statistics
Administration of prior medication (diabetic drug)	No, Yes
Prior medications (diabetic drugs)	
α-glucosidase inhibitors, thiazolidines, sulfonylureas, biguanides, rapid-acting insulin secretagogues, insulin preparations, DPP-4 inhibitors, GLP-1 receptor agonists, SGLT2 inhibitors, combination of diabetic drugs, or other diabetic drugs
 
For the proportion, the number of patients with “Yes” for administration of prior medication (diabetic drug) will be denominator.

Administration of prior medication (other than diabetic drug)	No, Yes
Administration of concomitant medication (diabetic drug)	No, Yes
Concomitant medications (diabetic drugs) (overlapped)	
α-glucosidase inhibitors, thiazolidines, sulfonylureas, biguanides, shortrapid-acting insulin secretagogues, insulin preparations, DPP-4 inhibitors, GLP-1 receptor agonists, SGLT2 inhibitors, combination of diabetic drugs, or other diabetic drugs
 
For the proportion, the number of patients with “Yes” for administration of concomitant medication (diabetic drug) will be denominator.

Administration of concomitant medication	No, Yes

Parameter	Category
(hypertension drug)	
Concomitant medications (hypertension drugs) (overlapped)	ARB, Ca antagonists, ACE inhibitors, diuretics, α blockers, $\alpha\beta/\beta$ blockers, Complication of hypertension drugs, or other For the proportion, the number of patients with “Yes” for administration of concomitant medication (hypertension drug) will be denominator.
Administration of concomitant medication (dyslipidaemia drug)	No, Yes
Concomitant medications (dyslipidaemia drugs) (overlapped)	Statins, fibrates, EPA/DHA, or other For the proportion, the number of patients with “Yes” for administration of concomitant medication (dyslipidaemia drug) will be denominator.
Administration of concomitant medication (protease drug)	No, Yes
Administration of concomitant medication (combined with renal excretory drug)	No, Yes

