6.4 Changes in HbA1c, etc. by Factor Probably Affecting Efficacy

(1) Patients to be tabulated and analyzed

Efficacy Analysis Set

(2) Details of tabulation and analysis

For changes in HbA1c (NGSP values), summary statistics and the mean 95% confidence intervals will be calculated and the paired t-test will be performed at each testing time point (start of Nesina treatment, 3 months, 6 months, 12 months, 24 months, and 36 months after Nesina treatment and last evaluation).

The Glycemic control achievement rate for HbA1c ($< 7.0\%$, $\geq 7.0\%$ / $< 6.0\%$, $\geq 6.0\%$) at each testing time point (start of Nesina treatment, 3 months, 6 months, 12 months, 24 months, and 36 months after Nesina treatment and last evaluation) will be tabulated at the following parameters:

i Sex (Male, Female)

ii Age (< 65 years, ≥ 65 years)

iii Age (< 75 years, ≥ 75 years)

iv Concurrent renal disorder (No, Yes)

v HbA1c (NGSP value) at the start of Nesina treatment ($< 6.0\%$, 6.0% to $< 7.0\%$, 7.0% to $< 8.0\%$, $\geq 8.0\%$)

vi Mean daily dose of Nesina (> 25 mg, 25 to > 12.5 mg, 12.5 to > 6.25 mg, or 6.25 mg)

vii Concomitant diabetic drugs (α -glucosidase inhibitors, thiazolidines, sulfonylureas, biguanides, rapid-acting insulin secretagogues, or insulin preparations)

(3) Number of tables and figures

Tables 6.4-1 to 6.4-14

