Patients with concurrent allergic rhinitis	Patients with concurrent disease of the PT Code 10039085 (rhinitis allergic).
Patients with concurrent allergic dermatitis	Patients with concurrent disease of the PT Code 10012434 (dermatitis allergic).
Patients with concurrent malignant tumor	Patients with concurrent disease of the SOC Code 10029104 (neoplasms benign, malignant and unspecified (incl cysts and polyps)).
Patients with concurrent malignant tumor (narrow sense)	Patients with concurrent disease of the SMQ Code 20000194 (malignant tumour (SMQ) narrow).
Patients with other concurrent disease	Patients with concurrent disease other than the above (diabetic complication, hypertension, dyslipidaemia, hyperuricaemia, liver disease, renal disease, heart disease, stroke-related disease, allergic disease, malignant tumor, or malignant tumor (narrow sense)).
Severity of renal impairment	Severity of renal impairment in the patient demographic section

Term	Definition
Age	If the start month and date of Nesina treatment is earlier than the birth month and date, calculate using the following formula: Start year of Nesina treatment – birth year – 1. If the birth month and date is earlier than or equal to the start month and date of Nesina treatment, calculate using the following formula: Start year of Nesina treatment – birth year. For unknown birth date, the birth date will be calculated as the 1st day of the birth month.
BMI	Calculate using the following formula: Weight (kg) / (0.0001 × Height (cm) × Height (cm)). Indicate to one decimal place rounded from two decimals.
Disease duration of type 2 diabetes mellitus (year)	Calculate using the following formula: (start date of Nesina treatment – diagnosis period of type 2 diabetes mellitus + 1) / 365.25. For unknown diagnosis month, calculate as January. Indicate to one decimal place rounded from two decimals.
Prior medication	Medications that patients were taking within 3 months before initiation of Nesina therapy.
Concomitant medication	Medications that patients were taking after the start date of Nesina treatment.
Start date of other diabetic drug and concomitant medication (other than diabetic drug)	Calculate as the start date of survey sheet (electronic).
End date of other diabetic drug and concomitant medication (other than diabetic drug)	Calculate as the end date of survey sheet (electronic).

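### SAP 6.4 factor vii can file an HbA1c change at months 3 to 24 under a diabetic drug begun only after that visit

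*SAP*

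**What the plan says.** SAP 6.4 gives summary statistics, a 95% confidence interval and a paired t-test for HbA1c change, plus achievement rates, at these points: "start of Nesina treatment, 3 months, 6 months, 12 months, 24 months, and 36 months after Nesina treatment and last evaluation". One of the factors is "vii Concomitant diabetic drugs", with six classes: α-glucosidase inhibitors, thiazolidines, sulfonylureas, biguanides, rapid-acting insulin secretagogues and insulin.

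SAP 1.1 defines concomitant medications as "Medications that patients were taking after the start date of Nesina treatment". It sets no window. SAP 1.5 says which visit data count, but nothing about drug timing. All three SAP texts supplied agree on these points.

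The data needed for a tighter rule exist. Protocol 9.3 collects, for each other diabetic drug, "drug name, daily dose, route of administration, and administration period", from the start of Nesina to month 36 or discontinuation. SAP 1.1 takes drug start and end dates from the survey sheet, and defines prior medication separately. Factor vii uses none of these.

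Protocol 10.5.2 names month 36 as the time point for the efficacy stratification. The earlier visits are added by the SAP.

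**The concern.** Taken together, the factor and the definition mean that one record of use at any time after Nesina start places a patient in a class row for every visit. A patient who adds a sulfonylurea at month 30 is in the sulfonylurea row at months 3, 6, 12 and 24, before taking any. At month 3 the drug may lie up to 36 − 3 = 33 months ahead.

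If drugs are added because HbA1c has risen, class membership depends partly on the later course of the same HbA1c series that the row reports. The early rows then mix two groups: patients who combined Nesina with the drug from the start, and patients selected later for losing control. A reader would take such a row as the early response to Nesina plus that class, and it would tend to look poorer than it was.

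**Working it through.** **Planned group sizes.** Protocol 3.2 gives database counts of 1864 (diet and exercise only), 226, 175, 273 and 109, which sum to 2647. Scaling by 20000/2647 gives 14083.9, 1707.6, 1322.3, 2062.7 and 823.6. These reproduce the stated 14084, 1708, 1322, 2063 and 824. The four combination groups total 1708 + 1322 + 2063 + 824 = 5917.

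**Share of later starters in the pooled drug rows.** Let x be the fraction of the 14084 who later add a drug (assumed). The share is w = 14084x / (14084x + 5917). At x = 10%, for example, 1408.4 / 7325.4 = 19%. If a quarter of the starters take a biguanide (assumed), their share of that row is 0.25 × 14084x / (0.25 × 14084x + 824).

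**Month-3 shift.** Suppose the later starters are the fraction x with the worst later control, and later control has correlation r with month-3 change. Assume an SD of change of 0.6 and the same true mean in all classes. The pooled row then moves by w × r × 0.6 × φ(z)/x, where z is the upper-x normal quantile.

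| x | φ(z)/x | w, pooled rows | Share, biguanide row | Pooled shift, r = 0.2 to 0.6 |
|---|---|---|---|---|
| 5% | 2.06 | 11% | 18% | 0.03 to 0.08 |
| 10% | 1.76 | 19% | 30% | 0.04 to 0.12 |
| 20% | 1.40 | 32% | 46% | 0.05 to 0.16 |
| 30% | 1.16 | 42% | 56% | 0.06 to 0.17 |

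At r = 0 the shift is zero. Simulation of 200 cohorts of 20000, with a true change of −0.40 for everyone, agrees. With r = 0.4 the pooled rows show −0.32 at x = 10% and −0.29 at x = 20%.

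**A second model.** Here a drug is added with probability 0.5 at each visit reading of 7.4% or more. All inputs are assumptions:
- true HbA1c mean 6.8%, SD 0.45, with entry at 7.4% or below;
- Nesina effect −0.3, SD 0.3;
- drift +0.05 per year, SD 0.10;
- within-patient SD 0.2.

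About 10% ever add a drug. At month 3, before anyone has taken one, later starters average +0.11 and all patients −0.27. With a 19% share the pooled row shows 0.19 × 0.11 + 0.81 × (−0.27) = −0.20, a shift of about 0.07. With the 30% biguanide share it is 0.30 × (0.11 + 0.27) = 0.11.

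**Sensitivity of the second model.** The gap between later starters (+0.11) and the rest (−0.31) is 0.42. With a response SD of 0.1 the means are −0.11 and −0.28, a gap of 0.17. With no Nesina effect in any patient they are +0.10 and +0.01, a gap of 0.09. At month 12 the later starters' mean is +0.20 if the added drug does nothing, and about +0.07 if it lowers HbA1c by about 0.5. The late-visit size therefore depends on a further unknown.

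**The case against.** The strongest reply is that this is one factor in a secondary, descriptive stratification of a single-arm surveillance, and that the protocol's own time point escapes the problem. Drug use is recorded to month 36, so at that visit a recorded drug has already begun. That stands for month 36, although users from the start and later users are still pooled there. It does not help the earlier visits that the SAP adds.

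Second, factor vii has no row for patients without other drugs and no test between classes, so no planned output contrasts ever-users with the rest. That is correct, which is why the working measures the shift within a row. The ever-versus-rest gaps show sensitivity only.

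Third, SAP Table 4.0-1 shows prior and concomitant classes separately, so a reader can gauge how common later starts were. That helps interpretation but does not correct the rows.

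A reader might go further and infer that the class rows fill with poor responders, or that every combination will look less effective at every visit. The documents do not support either. They give no add-on rate and no link to early response, and an effective added drug could narrow or reverse the shift at late visits. Nor does the problem reach every diabetic drug: DPP-4 inhibitors, GLP-1 receptor agonists and SGLT2 inhibitors have no row in factor vii.

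**Conclusion.** Factor vii is wrong as written for months 3 to 24. The plan states a rule, and following it classifies an early HbA1c change by a later drug. The mechanism follows from the text alone. The direction, towards a poorer response, needs the further assumption that drugs are added for lost control.

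The size rests on assumed add-on rates, correlations and SDs, and on the planned group sizes being realised. In that range the pooled month-3 shift is 0.03 to 0.17 percentage points, about 0.07 at 10% add-on in the second model, and zero if add-on is unrelated to early response. It is larger where few patients use the class at the start. Protocol 3.2 plans no at-start group for insulin or rapid-acting secretagogues, so their share of later starters cannot be computed. The overall HbA1c analysis in SAP 6.1 does not use the classes and is unaffected.

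**What to change.** In SAP 6.4 factor vii, define the class by the diabetic drugs in use on the first date of Nesina treatment, using the administration period collected under Protocol 9.3. Keep that class for every time point. If later additions are to be shown, give them a separate row per visit, limited to drugs started on or before that visit. No visit should be classified by a drug begun after it.

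The cost is a sentence in the SAP and one derived variable, with no new data. The class rows become smaller: under the planned sizes, the four combination groups return to 5917 patients. SAP 5.16 and 5.17 split adverse reactions with the same definition and should be checked at the same time.
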